## **Ibudilast Withdrawal Protocol Study Design**

### **Specific Aims**

Alcohol use disorder (AUD) is a prevalent and disabling psychiatric disorder with few, and only moderately efficacious, treatment options. Consequently, the identification of novel treatment targets and the development of rigorous laboratory paradigms to screen and optimize novel therapeutics represents a research priority. Ibudilast (IBUD) is a neuroimmune modulator that inhibits phosphodiesterase-4 and -10 and macrophage migration inhibitory factor. Recently in an AUD sample, IBUD was shown to decrease reactivity to a psychological stressor. Furthermore, IBUD was effective in blunting alcohol reward among participants with greater depressive symptoms, a hallmark symptom of protracted withdrawal. It is still unknown how neuroimmune modulation impacts brain processes that underlie alcohol reward processing. Recently, preclinical research in opiates has demonstrated that drug withdrawal is necessary for microglia activation and neuroinflammation in reward networks, suggesting that IBUD may be most effective among patients who experience withdrawal-related dysphoria. Therefore, this proposed study aims to examine withdrawal-related dysphoria as a moderator of IBUD efficacy in the natural environment measured using Daily Diary Assessment (DDA) approaches. To accomplish this aim, participants meeting criteria for AUD and balanced on the presence of withdrawal-related dysphoria will be enrolled in a double-blinded IBUD trial including consisting of two weeks randomized to medication, DDA assessment, and fMRI. The proposed research aims are:

**Aim 1:** Test whether IBUD reduces basal negative affect in abstinence and blunts alcohol-related negative reinforcement. It is hypothesized that IBUD will reduce basal levels of negative affect during alcohol abstinence, and in so doing will interfere with alcohol-induced blunting of negative affectivity as captured during naturalistic drinking episodes.

**Aim 2:** Test whether IBUD attenuates neural alcohol cue-reactivity. It is hypothesized that IBUD will reduce BOLD activation to alcohol cues in mesocorticolimbic reward circuitry.

**Aim 3:** Test whether withdrawal-related dysphoria moderates the effects of IBUD. It is hypothesized that IBUD will alleviate basal negative affect, interfere with alcohol-induced negative reinforcement and attenuate BOLD activation to alcohol cues only among participants who experience dysphoria in withdrawal.

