**Aim 4:** Test whether neural activation to alcohol cues is predictive of drinking outcomes. It is hypothesized that individuals with higher mesocorticolimbic activation to alcohol cues will report more drinking in the week following the neuroimaging session.

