## IBUD Withdrawal Protocol

Version 4, 05/10/18

6. A 30-day alcohol, cigarette, and marijuana timeline follow-back (TLFB)
7. Reasons for Heavy Drinking Questionnaire (RHDQ)
8. Reward-Relief Drinking Scale (RRDS)
9. The Alcohol Dependency Scale (ADS)
10. The Alcohol Use Disorders Identification Test (AUDIT)
11. Family Tree Questionnaire (FTQ)
12. Fagerstrom Test for Nicotine Dependence (FTND)
13. Beck Depression Inventory-II (BDI-II)
14. Pain Catastrophizing Scale (PCS)
15. Graded Chronic Pain Scale (GCPS)
16. RTC Ladder
17. Snaith-Hamilton Pleasure Scale (SHAPS)
18. Penn Alcohol Craving Scale (PACS)
19. Obsessive Compulsive Drinking Scale (OCDS)
20. Concomitant Medications Assessment
21. Center for Cognitive Neuroscience MRI Safety Screening Form

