#### *Midpoint Functional Brain Imaging*

After the midpoint measures (above) are collected, participants will complete a brain functional magnetic resonance imaging (fMRI) scan. The scanning will be performed at the Brain Mapping Center or at the Center for Cognitive Neuroscience, both located on the UCLA campus. They will be asked to lie down on a padded table, with their head placed in the center of a large, metal doughnut-shaped magnet. While the machine is running, the participant will hear loud banging noises and will be offered earplugs to reduce the noise made by the magnet. Head and back support will also be provided to minimize discomfort.

[figure not shown]
Participants will be asked to have a normal night's sleep the night before the scan, have no more than one alcoholic drink, and abstain from drinking coffee within 2 hours prior to the scan. Breath alcohol concentration must be zero and for female participants the pregnancy test must be negative immediately prior to the scanning session. Prior to scanning, subjects will practice the task in front of a computer monitor with headphones and a button response box using the same stimulus delivery software as for fMRI scanning. The subjects will practice until it can be ascertained that they understand the task.

During the imaging session we will utilize several structural and functional scans. The structural protocol will consist of a high-resolution, matched-bandwidth (MBW) scan and a structural magnetization-prepared rapid-acquisition gradient echo (MPRAGE) scan. The functional scan will include a fMRI alcohol-cue reactivity paradigm previously reported to elicit blood oxygen level dependent (BOLD) response in mesocorticolimbic regions (Schacht et al., 2011).

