IBUD's effects on neural alcohol cue-reactivity will be analyzed using FSL's FEAT (<https://fsl.fmrib.ox.ac.uk/fsl/fslwiki/FSL>). The following preprocessing steps will be used: 1) FSL'S MCLFIRT will be used for motion correction; 2) FSL's BET will be used for non-brain tissue and skull removal; 3) Data will be spatially smoothed using a Gaussian kernel of FWHM 8mm; 4) Data will be mean-based intensity normalized; and 5) Data will undergo highpass temporal filtering. Explanatory variables will be created by convolving the stimulus timing files with a double gamma hemodynamic response function. Contrast maps will be created by contrasting alcohol and neutral beverage cues. After transforming the masks into standard MNI space, higher-level analysis will be carried out and Z-statistic images will be thresholded using GRF-theory-based maximum height thresholding with a significance of one-tailed $p < 0.05$. Hierarchical linear modeling (HLM) will be used to test for a medication effect. Cue type will be denoted by dummy-coded variables representing contrasts between alcohol and neutral beverage cues. The second level predictor will be medication condition (IBUD vs. placebo). The main approach is to test, at the whole-brain significance level, the effects of medication condition on BOLD activation generated during the alcohol cue reactivity paradigm.

Aim 3: Moderating Effects of Withdrawal-Related Dysphoria

To test whether the presence of withdrawal-related dysphoria (WRD) predicts a greater response to IBUD, a series of multilevel models will be conducted building on the models analyzed in Aim 1. Specifically, in these models we will test the moderating effects of WRD, a binary between-subjects factor on IBUD effects through the inclusion of the Medication \times WRD interaction. A significant interaction between Medication \times WRD, or Medication \times WRD \times Alcohol will be interpreted as evidence that the presence of withdrawal related dysphoria is an important predictor of the clinically relevant effects of IBUD.

Aim 4: Neural Cue Reactivity as a Predictor of Future Drinking

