To test whether neural alcohol cue reactivity can predict drinking in the week following neuroimaging, we will conduct a correlational analysis. We will calculate the number of drinks per drinking day for the 7 days following the Day 8 mid-point neuroimaging visit from the DDA data. We will also derive the maximum percent signal change from the whole brain fMRI analyses using Featquery (part of FSL's FEAT). This signal will be derived from the alcohol versus control cue contrast. For Primary Aim 2a, we will compute correlations between the number of drinks per drinking day and the whole brain percent signal change values using SAS Statistical Software.

Exploratory Aims:

Additional models analogous to those outlined for Aim 1 and Aim 3 will be conducted on the following outcomes: Positive Mood (POMS) and Craving (AUQ) assessed in daily diary reports, Withdrawal-Related Dysphoria (RHDQ) during alcohol abstinence, and Stimulation and Sedation (B-BAES).

Citations

- [1] Charles A. Scherbaum and Jennifer M. Ferrerter, "Estimating Statistical Power and Required Sample Sizes for Organizational Research Using Multilevel Modeling," *Organ. Res. Methods*, vol. 12, no. 2, pp. 347–367, Apr. 2009.
- [2] R Development Core Team, *R: A Language and Environment for Statistical Computing*. Vienna, Austria: R Foundation for Statistical Computing, 2008.
- [3] P. Bliese, *multilevel: Multilevel Functions*. 2013.
- [4] L. A. Ray, S. Bujarski, P. F. Chin, and K. Miotto, "Pharmacogenetics of Naltrexone in Asian Americans: A Randomized Placebo-Controlled Laboratory Study," *Neuropsychopharmacology*, vol. 37, no. 2, pp. 445–455, Jan. 2012.
- [5] S. Bujarski, J. MacKillop, and L. A. Ray, "Understanding naltrexone mechanism of action and pharmacogenetics in Asian Americans via behavioral economics: A preliminary study.," *Exp. Clin. Psychopharmacol.*, vol. 20, no. 3, pp. 181–190, Jun. 2012.
- [6] R. Miranda *et al.*, "Biobehavioral mechanisms of topiramate's effects on alcohol use: an investigation pairing laboratory and ecological momentary assessments," *Addict. Biol.*, p. n/a-n/a, Nov. 2014.

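### Aim 4 hypothesises that mesocorticolimbic activation predicts drinking, but the planned predictor is a maximum from the whole-brain analyses, and neither document defines a mesocorticolimbic region

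*SAP*

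**What the plan says.** The protocol's Specific Aims state the Aim 4 hypothesis as "individuals with higher mesocorticolimbic activation to alcohol cues will report more drinking in the week following the neuroimaging session". Aim 2 names the same circuitry: "IBUD will reduce BOLD activation to alcohol cues in mesocorticolimbic reward circuitry".

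The SAP's Aim 4 section builds the predictor differently. It will "derive the maximum percent signal change from the whole brain fMRI analyses using Featquery", using the alcohol-versus-control contrast. It then says "we will compute correlations between the number of drinks per drinking day and the whole brain percent signal change values", so the whole-brain wording appears twice.

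Three other places might have supplied a region:

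- The protocol's Midpoint Functional Brain Imaging section says only that the task was "previously reported to elicit blood oxygen level dependent (BOLD) response in mesocorticolimbic regions". It lists no regions.
- The SAP's Aim 2 section mentions masks once: "After transforming the masks into standard MNI space, higher-level analysis will be carried out". It does not say what they are or where they come from.
- The same section sets the level of inference for the medication effect: "The main approach is to test, at the whole-brain significance level, the effects of medication condition on BOLD activation".

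**The concern.** The hypothesis names a circuit and the measure does not. A per-person maximum can come from a different place in each participant, and nothing in the plan ties it to mesocorticolimbic tissue.

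What is at stake is how the Aim 4 result can be read. If the correlation is positive, the peak may have been driven by a region outside the hypothesised circuitry. If it is null, the circuitry may still predict drinking but be poorly represented by the peak. An undefined region also leaves room to choose one after results are seen.

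**Working it through.** **Step 1. Search for a region.** The word mesocorticolimbic occurs in the protocol (Aims 2 and 4, and the imaging section) and nowhere in the SAP. Neither document gives anatomical regions, an atlas, coordinates or a named mask. Aim 2 is tested at whole-brain level, so Aim 4 cannot borrow a region from it.

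**Step 2. Two readings of the SAP predictor.**

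- *One maximum over the whole brain.* Its location is wherever the contrast is largest.
- *The peak within clusters that survive the Aim 2 threshold.* These clusters may lie in the circuitry, but the data choose them. If none survives, no predictor is defined.

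Neither reading fixes the location in advance.

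**Step 3. The plan's own power figure.** The only one is 68% at N = 50 for the medication main effect. Taking two-sided 5% and 1:1 allocation as assumptions, SE = √(4 × (0.5 + 0.5/15)/50) = 0.207, and power = Φ(0.5/0.207 − 1.96) = 67.7%. It reproduces, but it does not concern Aim 4, which has no power statement.

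**Step 4. Illustrative size.** Every input here is assumed except N = 50.

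Power = Φ(√(n − 3) × atanh(0.40 × ρ) − 1.96), two-sided 5%, where ρ is the correlation of the chosen predictor with true regional activation.

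- Perfect measurement (ρ = 1), n = 50: Φ(6.856 × 0.4236 − 1.96) = 83%.
- Perfect measurement, n = 40: Φ(6.083 × 0.4236 − 1.96) = 73%.

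To obtain ρ, the brain is simulated as 500 or 2,000 independent resolution elements, 20 of them in the target. The between-person SD of target activation is 0.5 or 1.0, and the target's mean is raised by 1 or 2 units. In the first setting, element noise has SD 1 and only the target varies between people. There ρ is 0.30–0.66 (raised by 1) or 0.61–0.83 (raised by 2) for the whole-brain maximum, and 0.91–0.98 for the mask mean. For example, ρ = 0.30 gives Φ(6.856 × atanh(0.12) − 1.96) = 13%.

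| Assumed setting | Whole-brain maximum | Mean over a well-fitting mask |
|---|---|---|
| Noise SD 1, target raised by 1 | 13–46% | 74–81% |
| Noise SD 1, target raised by 2 | 40–66% | 74–81% |
| Noise SD 0.5, raised by 1 | 61–72% | 81–82% |
| Noise SD 0.5, raised by 2 | 72–79% | 81–82% |
| Noise SD 1, other regions carry half the person-level reactivity, raised by 1 | 44–69% | 75–81% |
| As above, raised by 2 | 47–71% | 75–81% |
| Noise SD 0.5 and half-shared reactivity | 71–80% | 81–82% |

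For the cluster reading, the best case is clusters that coincide exactly with the target. In the first setting the maximum within them gives 49–72%.

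**Step 5. False support (noise SD 1).** Suppose only a region outside the circuitry predicts drinking (r = 0.40). The whole-brain maximum is then significant in about 19–31% of trials if that region is as active as the target (each raised by 2), and in about 6–11% if it is 1 unit less active. The mask mean is significant in about 5%, the nominal level.

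**Step 6. When the mask does worse.** If a fraction f of the mask overlaps the responding region, the mask mean has ρ = f·s/√(f²s² + 1/20), with s the between-person SD and noise SD 1. Setting this equal to the maximum's ρ gives f = ρ/(s√(20(1 − ρ²))). With s = 0.5 and ρ = 0.61, f = 0.61/(0.5 × √12.56) = 0.34. Across the first two rows of the table, break-even overlap is about 14–23% (raised by 1) and 28–38% (raised by 2). With half overlap, the mask mean still has 55–75% power.

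**The case against.** A reader might infer that the plan, followed exactly, tests something other than its hypothesis. The documents do not support that much. The SAP wording also fits the peak within surviving clusters, and those could lie inside the circuitry. On that reading the defect is a region left unspecified, not a wrong one. This stands as a limit on the claim, but it does not rescue the plan, because the data would still pick the location.

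A reader might also infer a large, known loss of power. That is not supported either. The 13% figure is one corner of the assumptions. With lower noise and shared reactivity the maximum reaches 80% and the gap to the mask mean nearly closes. The direction survives: in no setting tried did the maximum beat a well-fitting mask. Shared reactivity narrows the power loss but does not restore regional specificity.

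The whole-brain approach is openly declared, but for the medication effect in Aim 2. It defines no per-person measure for a regional hypothesis.

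Finally, the SAP's power section calls the study exploratory, and Aim 4 is a single correlation that does not bear on the medication comparison. This limits the severity. Even so, the hypothesis is directional and regional, and the SAP labels the correlation as belonging to a primary aim.

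**Conclusion.** The point holds on the text alone. The stated predictor is not tied to the hypothesised circuitry, and no region is defined from which it could be. The correlation as planned can neither clearly support nor clearly refute the Aim 4 hypothesis.

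Its size cannot be established from the documents. The ranges of about 13–80% for the whole-brain maximum and 74–82% for a well-fitting mask mean depend on the assumed true correlation of 0.40, 50 usable scan–drinking pairs, and the assumed noise, elevation and shared reactivity. Fifty pairs is optimistic: the protocol withdraws participants who meet certain exclusion criteria after randomisation, and drinks per drinking day is undefined for anyone with no drinking day that week.

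This should be fixed, but it affects the interpretation of one aim only, not the medication comparison.

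**What to change.** In the SAP's Aim 4 section, name one a priori mesocorticolimbic mask, giving its atlas and regions, before unblinding and before scan data are linked to drinking data. Use the mean alcohol-versus-neutral percent signal change within that mask as the Aim 4 predictor. Keep the whole-brain maximum as exploratory, and say which of the two readings in Step 2 it has.

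If the sponsor really intends a whole-brain question, reword the protocol's Aim 4 hypothesis to match and limit the conclusion accordingly.

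The cost is SAP wording and one extraction from scans already planned, with no extra participants. The downside is that a mask mean misses effects outside the mask and can do worse than the maximum if the mask overlaps the responding region poorly (Step 6), so the choice of regions needs a stated rationale.

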### **Medication Administration**

Study medication and matched placebo will be provided by Medicinova Inc. and dispensed by the UCLA Health Pharmacy Investigational Drug Section who will also maintain the blind. After establishing eligibility, participants will be provided with their first medication dosage in a blister-pack. IBUD will be provided in 10 mg capsules and participants will be titrated as follows: 20 mg BID during days 1-2, 50 mg BID during days 3-14, or matched placebo. All capsules will contain a riboflavin (50 mg) tracer to verify compliance. EMA assessment will begin on Medication Day 1 and will continue through Day 15 (one day post medication termination).

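### Aim 4 correlates on-treatment cue reactivity with on-treatment drinking without a term for arm or prior drinking, so it can show marginal association but not prediction within arms or beyond drinking history

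*SAP*

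**What the plan says.** The Protocol (Specific Aims, Aim 4) hypothesises that "individuals with higher mesocorticolimbic activation to alcohol cues will report more drinking in the week following the neuroimaging session". The SAP (Aim 4) takes as outcome the "number of drinks per drinking day for the 7 days following the Day 8 mid-point neuroimaging visit", derives a maximum percent signal change from the alcohol versus control contrast, and then states that "we will compute correlations between the number of drinks per drinking day and the whole brain percent signal change values". It names no medication term, by-arm analysis, partial correlation or drinking covariate.

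Four other places bear on this:

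- Protocol, Medication Administration: capsules are taken as "20 mg BID during days 1-2, 50 mg BID during days 3-14, or matched placebo", and the diary runs one day longer, to Day 15.
- Protocol, Specific Aims, Aim 2: "It is hypothesized that IBUD will reduce BOLD activation to alcohol cues in mesocorticolimbic reward circuitry". The SAP models medication in Aims 1 to 3.
- Protocol, Behavioral Screen Measures: a 30-day timeline follow-back (TLFB) of alcohol use is collected. The SAP gives it no role in Aim 4.
- SAP, Random Assignment Checks: variables found to differ between arms at pretest, drinking history among those checked, become covariates in later analyses.

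**The concern.** The only scan the Protocol describes is the midpoint one, so there is no drug-free measure of cue reactivity. A correlation across all participants can therefore draw on three sources: a link between cue reactivity and drinking within each arm, a difference between arms on both measures, and stable drinking severity that raises both. The planned analysis does not separate them.

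The general covariate rule does not close the gap. It can never add arm, and it adds prior drinking only if the arms happen to differ on it. Whether prior drinking lies behind both the scan result and later drinking has nothing to do with its balance between arms.

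What is at stake is the interpretation of Aim 4. A significant correlation could be reported as evidence that the scan carries information about future drinking when a drinking history, or knowledge of the arm, would have given the same information.

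**Working it through.** **Timing.** The seven days after Day 8 are Days 9 to 15. Dosing covers Days 1 to 14, so the scan and six of the seven outcome days are on treatment.

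**The plan's own figure.** The SAP gives no power figure for Aim 4. Its one figure, 68% at N = 50, concerns the medication main effect (effect 0.5, 15 observations per subject, ICC 0.5). Assuming equal arms and two-sided 5%, the variance of a subject mean is 0.5 + 0.5/15 = 0.533, the standard error is √(4 × 0.533/50) = 0.207, and power is Φ(0.5/0.207 − 1.96) = Φ(0.46) = 68%. It reproduces. Its only use here is to supply the one medication effect size in the documents, d = 0.5.

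**Reference points for a correlation at N = 50.** Two-sided p < 0.05 needs |r| above 0.279. Power of 80% needs r of about tanh((1.96 + 0.84)/√47) = 0.39.

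**Correlation induced with no direct link.** Let medication shift cue reactivity and drinking by d₁ and d₂ (within-arm SD 1, equal arms), and let prior drinking correlate a with cue reactivity and b with later drinking. Then

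r = (d₁d₂/4 + ab) / √[(1 + d₁²/4)(1 + d₂²/4)].

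The chance of p < 0.05 follows from Fisher's z with standard error 1/√47.

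- Arm alone, d = 0.5 on both: 0.0625/1.0625 = 0.06, about 7%.
- Arm alone, d = 0.8 on both: 0.16/1.16 = 0.14, 16%.
- Arm alone, d = 1.0 on both: 0.25/1.25 = 0.20, 28%.
- Prior drinking alone, a = 0.3, b = 0.6: 0.18, 24%.
- Prior drinking alone, a = 0.3, b = 0.7: 0.21, 31%.

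**Check by simulation.** There were 20,000 runs per scenario with normal data, 25 per arm, and no association given arm and prior drinking. The last three columns give the percentage of runs with p < 0.05.

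| Assumed common cause | Induced r | Plain | Adjusted for arm | Adjusted for arm and prior drinking |
|---|---|---|---|---|
| Arm, d = 0.5 on both | 0.06 | 6.7 | 4.9 | 4.8 |
| Arm, d = 0.8 on both | 0.14 | 15.8 | 5.0 | 5.0 |
| Prior drinking 0.3, 0.5 | 0.15 | 18.2 | 18.0 | 4.9 |
| Prior drinking 0.3, 0.7 | 0.21 | 31.3 | 30.7 | 5.1 |
| Prior drinking 0.5, 0.7 | 0.35 | 72.0 | 71.1 | 5.0 |
| Arm d = 0.5 on both, plus 0.3, 0.7 | 0.26 | 44.3 | 31.3 | 4.9 |
| Arm d = 0.5 in opposite directions, plus 0.3, 0.7 | 0.14 | 15.8 | 30.8 | 5.0 |

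Adjusting for arm alone leaves the prior-drinking part in place; both covariates are needed. The last row shows that opposite medication effects pull the pooled correlation down (0.14 against 0.21), so pooling can also hide an association.

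Every d, a and b here is an assumption. Only d = 0.5 has a counterpart in the SAP, and there it refers to a different outcome.

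**The case against.** The strongest objection is that Aim 4, as worded, is a statement of marginal association: people with more activation will report more drinking the next week. A correlation tests that directly, and a marker that shares a cause with a later outcome does predict it. This stands. The percentages above are error rates only for the narrower claim of prediction independent of arm and drinking history; for the marginal claim, the correlations of 0.18 to 0.21 are real.

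The medication path is weak on the plan's own terms. At d = 0.5 it adds about two percentage points to the nominal 5%, and it requires an ibudilast effect on drinks per drinking day, which no aim states. This stands too. Prior drinking is the larger part of the point, although its size rests wholly on assumed correlations.

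The SAP does not say that the arms are pooled. That is an inference from its silence, though the natural one. If a by-arm analysis is intended, the SAP should say so.

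Adjusting for arm has a price. If ibudilast reduces drinking by reducing cue reactivity, the difference between arms is part of the true link, and the adjusted estimate leaves it out. This is a reason to keep both results rather than replace one with the other.

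Finally, the SAP calls the study exploratory. That lowers the stakes, but Aim 4 is a listed aim with a directional hypothesis and is not among the SAP's separate exploratory aims.

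**Conclusion.** The point holds for interpretation. As specified, Aim 4 can support a statement that cue reactivity and next-week drinking are associated in this sample. It cannot support a statement that cue reactivity predicts drinking within arms or adds to drinking history.

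With N = 50 and equal arms, both sizes resting on assumed effects, the induced correlation is small through medication at d = 0.5 (r = 0.06, about 7% significant) and moderate through prior drinking at 0.3 and 0.6 to 0.7 (r = 0.18 to 0.21, 24 to 31% significant).

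A reader might go further and infer that the planned correlation is invalid, that a significant result would be a false positive, or that medication confounding alone could produce the finding. The documents do not support this. The marginal hypothesis is legitimately tested by a correlation. Arm effects large enough to matter alone (d = 0.8 to 1.0 on both measures) are nowhere suggested, and no aim expects ibudilast to change drinks per drinking day.

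**What to change.** Add to the SAP, Aim 4:

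- Keep the correlation and label it the marginal association over all participants.
- Add a linear regression or partial correlation of post-scan drinks per drinking day on percent signal change, adjusted for randomised arm and for pre-randomisation drinks per drinking day from the 30-day TLFB. Name that covariate explicitly, so that it is on the same scale as the outcome.
- Base any claim of prediction independent of treatment and drinking history on the adjusted coefficient.
- Show the correlation within each arm descriptively; with about 25 per arm under equal allocation, these are too imprecise for inference.

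The cost is a few lines of text and two degrees of freedom (48 to 46 with complete data). No new data are needed. The report should say that the adjusted estimate excludes any part of the link that runs through the difference between arms. The change does not make up for the absence of a pre-treatment scan, which is a feature of the design.
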